- A. **MDD patients: 25 patients** (ages 18-50) with unipolar MDD (single episode or recurrent) will participate. We will specifically recruit unmedicated patients. At enrollment, patients must be medication free for a period consistent with four half-lives of the drug in question (e.g. 4 weeks for fluoxetine). Diagnoses of MDD will be made by each patient's referring physician, or, in the case that there is not a referring physician, will be made by the PI (a board certified psychiatrist) with DSM-IVR criteria using the Structured Clinical Interview (SCID).⁶⁵ Patients will also be required to score ≥ 18 ⁷ on the 24 item version of the Hamilton Depression Rating Scale (HDRS).²⁴ All psychometric assessments will be performed by a trained technician. Patients with any of the following issues will be excluded: bipolar disorder, schizoaffective disorder, active suicidal ideation, or any history of psychosis. Given the high co-morbidity, concurrent anxiety disorders will be allowed, provided MDD is the major diagnostic consideration.
- B. **Healthy subjects: 25 healthy controls** (ages 18-50) will also be recruited. These subjects will be matched to MDD patients on the basis of age, gender and ethnicity. Controls must score ≤ 8 on the HDRS. These subjects must not meet criteria for any Axis I disorder (confirmed by DSM-IV criteria and by the SCID questionnaire), have no formal history of these, and must not be on any psychotropic medications.
- C. **Exclusion Criteria (All Subjects)**
 1. A history of serious concurrent medical or neurological illness, especially any patient with a known space-occupying lesion in the brain/skull.
 2. Concurrent substance use, abuse or dependence.
 3. Contraindications to receive MRI scanning including, but not limited to the presence of metallic or ferromagnetic implants (e.g. pacemaker, defibrillator, vagal nerve stimulator, implantable pump, metallic tattoos and/or make-up, surgical aneurysm clips, etc.); or severe claustrophobia.
 4. Contraindications to undergo PET scanning, e.g. a history of receiving radiation exposure with PET within the past 12 months.
 5. Contraindications to receiving TMS, specifically a history of seizures/epilepsy in the subject or in a first-degree relative or history of unexplained syncope.
 6. Any subject who is pregnant (as assessed by a STAT quantitative serum hCG test) or currently lactating.

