7. Any subject who has known metallic or ferromagnetic bioimplants, or who has a history of seizures or a first degree relative with seizures, or who has a history of significant claustrophobia.
- D. *Sample Size Determination:* Sample size calculations for the rTMS/fMRI studies are based on Eldaief et al, as we are unaware of other studies that provide empirical estimates of effect size. The main outcome measure for the TMS/fMRI experiments will be a change (pre vs. post-rTMS) in correlation values (z) between sgACC and DLPFC. Our study of 17 subjects yielded an effect size of 0.15 for 20Hz rTMS induced changes between lplPL and mPFC (SD=0.11). Based on this, sample sizes of 8 and 12 would have enough power (90%) to detect changes similar to those observed in our prior study at a significance level of 5% using an unpaired t-test or a paired t-test, respectively. With respect to PET, a comparable FDG-PET study⁶⁶ found an average change in rCMRglu of 5.3% (SD=2.77%) following high frequency rTMS. Based on this, sample sizes of 5 and 7 would be required (power, 90%; α , 0.05; unpaired and paired t-tests, respectively). However, because these effect sizes were all calculated from healthy controls, they might represent underestimates of the effect sizes needed for MDD patients. Therefore, we will conservatively recruit 25 subjects for each subject group.

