 3. Patients of [name] (co-investigator) who present to the MGH Depression Clinical Research Program (DCRP) with symptoms of major depression.

In the latter two cases, the PI will strongly emphasize that study participation is voluntary and that subjects' decisions to not participate will in no way affect their care with said investigator or their future care at any Partners institution.

Once identified as potentially eligible, subjects will undergo the aforementioned telephone screening/email assessments with the PI to further delineate their eligibility.

IV. SUBJECT ENROLLMENT

- A. Subjects will be randomized as to the order of the TMS sessions they undergo (there are two types of sessions in which one of two sites on the prefrontal cortex is stimulated). The order of these sessions will be counterbalanced across subjects. In other words, we will alternate between the two types of sessions and will have equal numbers of subjects having undergone a particular order of sessions. This will allow us to account for order effects.

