Study procedures will first consist of completion of study questionnaires followed by experimental procedures. In order to ensure eligibility to participate, all subjects will complete a SCID and HDRS rating scale. These will confirm the existence/absence of major depression and the absence of comorbid psychiatric conditions. Other exclusionary criteria will be screened via non-structured clinical interviews. A subject's eligibility for safely receiving rTMS, PET and fMRI will be assessed by filling out the appropriate screening forms (see attachments). All of these procedures will be performed by [name] (PI) who is trained in administering these instruments and screening forms. Finally, women of childbearing age will undergo a STAT quantitative serum hCG to ensure that they are not pregnant.

C. Aim 1 and 2 Experimental Procedures

50 subjects (25 MDD patients and 25 matched controls) will each undergo three experimental visits. In addition, of these subjects a subset (no more than five) will be given the option to undergo a fourth experimental visit. During the first study visit, consent will be obtained. Following this, subjects will be assessed for eligibility by

Fig 5.

Experimental timeline. Baseline fMRI/PET done on visit 1. Subjects return days later for 2-3 more visits in which they have fMRIs before rTMS and fMRI/PET afterwards.

screening procedures mentioned above. If they are considered eligible, they will undergo a baseline scan during this visit.

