SCID questionnaire	X			
Hamilton Depression Rating Scale (HDRS)	X			
TMS screening form	X			
MRI screening form	X	X	X	X
STAT quantitative serum hcG	X	X**	X**	X**
TMS side effects questionnaire		X	X	X
Baseline fcMRI/FDG-PET without rTMS	X			
fMRI before and after rTMS; FDG-PET after rTMS		X	X	X

**Exact frequency of pregnancy testing will vary according to how far visits are apart

Table 1: Summary of study procedures by visit

VI. BIOSTATISTICAL ANALYSIS

fcMRI data: The main outcome measures of interest for fcMRI data will be the relative change in z-transformed correlation coefficients between two given cortico-limbic network regions of interest (ROIs), the difference between changes in these z-scores across conditions (e.g. correlated vs. anticorrelated stimulation), and this difference across subjects (e.g. MDD vs. controls). Six cortico-limbic regions of interest will be examined: DLPFC (the 2 stimulation sites), sgACC, dmPFC, NA and amygdala. Seed placement for sgACC will be based on MNI coordinates from other fcMRI studies.^{21,22} Anatomical location of other seeds will be determined on an individualized basis as the points of maximal positive correlation with sgACC (or negative correlation in the case of one of the DLPFC sites). Seeds will be spherical and 8mm³ in diameter. The primary correlation pair of

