interest will be DLPFC-sgACC. Based on prior studies,^{1-9,30} secondary correlation pairs of interest will be sgACC-dmPFC, sgACC-NA and sgACC-amygdala. fMRI data will be analyzed using a combination of software packages (e.g., FMRIB Software Library, FSL, Freesurfer, SPM) and custom software developed in the [name] (mentor) lab. These methods have been described in several other paradigms^{27-29,76,77} and were employed in Eldaief et al.¹⁴ We will apply a stringent in-house data quality control program to each dataset, described Yeo et al.,⁷⁸ to evaluate fMRI runs for low signal-to-noise and/or excessive head movement. Preprocessing will include global mean regression and temporal band-passing of data for signals >0.08 Hz. After preprocessing, region-to-region correlation strengths will be calculated with volumetric seed-based functional connectivity analyses: correlation maps will be produced by extracting the BOLD time course from a “seed” ROI in the brain, and then computing the Pearson's correlation coefficient (r) between that time course and the time course from all other brain voxels. Functional connectivity between two ROIs will be measured by r values, which will be transformed to the z distribution. Paired t-tests will directly compare changes in z scores before and after rTMS in a given individual, and two-sample paired t-tests will compare changes across conditions and across subjects.

FDG-PET data: MR-based motion estimates and a dual-echo ultrashort echo time MRI sequence (DUTE)⁷⁹ will be used for motion- and attenuation-correction of PET data, respectively. Other preprocessing steps will include image realignment, normalization to MNI space and smoothing. Weighted linear contrasts will then be used to identify changes in rCMRglu in the cortico-limbic regions of interest described above. Relative differences in normalized rCMRglu in these ROIs between the baseline PET scan and the post-rTMS PET scan within a given individual will be calculated on a voxel-by-voxel basis using a paired t-test. Two sample paired t-tests will compare rCMRglu changes across rTMS conditions, and across MDD patients and normals. The experimental PET and fMRI data revealing local and distributed impacts of TMS will also allow for computational analyses which will be developed with the supervision and guidance of [name] (advisor).

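### The MDD-versus-control comparison of changes is assigned a paired t-test although no patient-control pairs are defined; the target comparison also omits the session order that the protocol says it will account for

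*Protocol*

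**What the plan says.** Section VI, fcMRI data, lists among its outcome measures the difference in changes between stimulation conditions "and this difference across subjects (e.g. MDD vs. controls"). It then keeps a paired t-test for the pre/post change within an individual and adds that "two-sample paired t-tests will compare changes across conditions and across subjects". The FDG-PET paragraph repeats the label: "Two sample paired t-tests will compare rCMRglu changes across rTMS conditions, and across MDD patients and normals".

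On the groups, Section V.C says that "50 subjects (25 MDD patients and 25 matched controls) will each undergo three experimental visits". Section III.B says of the controls: "These subjects will be matched to MDD patients on the basis of age, gender and ethnicity". Section III.D gives sample sizes "using an unpaired t-test or a paired t-test, respectively".

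On session order, Section IV.A calls the order randomized and counterbalanced and explains: "In other words, we will alternate between the two types of sessions and will have equal numbers of subjects having undergone a particular order". It concludes: "This will allow us to account for order effects".

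**The concern.** A t-test is either two-sample or paired. Section VI gives one self-contradictory name to two different comparisons. For the two targets, each subject contributes both values, so a paired analysis is right. For MDD against controls, no subject contributes to both sides. A paired test can then be run only after someone decides which control belongs to which patient, and the protocol records no such decision.

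H1.3 (larger connectivity changes in MDD) and H2.4 (altered local and distributed changes in MDD) depend on this test. At stake are a p-value that changes with the pairing, room to choose the pairing after seeing the data, and the loss of a usable control whenever a patient is lost. Patients can be lost through the removal rules in Section VII or the scan quality control in Section VI.

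The order question is secondary. Section IV.A says that order will be accounted for, but no analysis in Section VI contains an order or period term. The stability check under Experimental Controls compares pre-rTMS scans by target, not by order.

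**Working it through.** **The plan's own figures.** Section III.D takes a connectivity change of 0.15 with SD 0.11, so d = 0.15/0.11 = 1.364, with 90% power and alpha 5% (two-sided assumed). The noncentral t gives n = 7.8, so 8, for a paired test. It gives 12.3 per group, so 13, for an unpaired test (12 by the normal approximation). The stated 8 and 12 therefore reproduce only with the unpaired and paired labels exchanged. That is a separate matter. What counts here is that the section foresees an unpaired test, and MDD against controls is the natural comparison for it in Section VI.

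**How far the p-value depends on the pairing.** Take 25 per group, equal sample variances and unpaired p = 0.05, so t = 2.011 on 48 df. If r is the sample correlation across the 25 chosen pairs, then

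paired t = 2.011 / √(1 − r), on 24 df.

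Under arbitrary pairing r has mean 0 and SD 1/√24 = 0.204, so about 95% of pairings have r between −0.40 and +0.40.

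- r = −0.40: t = 2.011/√1.40 = 1.70, p = 0.102
- r = 0: t = 2.011, p = 0.056
- r = +0.40: t = 2.011/√0.60 = 2.60, p = 0.016

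The critical value on 24 df is 2.064. A pairing falls below 0.05 when r > 1 − (2.011/2.064)² = 0.051, which happens in about 40% of pairings (0.051/0.204 = 0.25 SD above the mean). Simulation with 5,000 random pairings per data set agrees: central 95% of p from 0.015–0.017 to 0.100–0.105, and 39–42% of pairings below 0.05.

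**Average operating characteristics** (25 per group; 40,000 simulated trials; true difference 0.8 SD for power; the within-pair correlation is an assumption):

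| Within-pair correlation | Type I, paired | Type I, unpaired | Power, paired | Power, unpaired |
|---|---|---|---|---|
| 0 (arbitrary pairs) | 4.9% | 4.9% | 77.6% | 79.2% |
| 0.5 (effective matching) | 5.0% | 0.8% | 97.1% | 86.9% |

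The difference detectable with 90% power is 0.94 SD unpaired. It is 0.676 × √2 = 0.96 SD with arbitrary pairs.

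**Session order.** Let the period effect shift the within-subject target difference by ±π, in SDs of that difference. The documents give no period effect, so π = 0.5 and π = 1.0 are assumptions. The bias without an order term is π(n₁ − n₂)/(n₁ + n₂).

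- Split 13/12: bias is at most 1.0 × 1/25 = 0.04 SD. Type I error is 3.0% (π = 0.5) or 0.7% (π = 1.0). Power for a 0.67 SD effect is 86% or 72%, against about 89% with an order term.
- Split 18/7, a severe case: bias is 0.5 × 11/25 = 0.22 SD or 0.44 SD. Type I error is 14% or 30%. With an order term it stays at 5%.

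For fcMRI the outcome is a pre/post change within one session, so a stable shift between visits cancels and only a shift in the response to rTMS matters. For rCMRglu both post-rTMS scans are compared with the single visit 1 baseline, so a shift between visits 2 and 3 enters the target difference directly.

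**The case against.** The best defence is that the controls are matched and the groups equal in size. If the matching is one to one and the pairs are kept, a paired group test is valid. With a within-pair correlation of 0.5 it is clearly the better test (97.1% against 86.9% power). This stands as far as the remedy goes: defining the pairs is as acceptable as dropping the pairing. It does not rescue the text, because Section III.B names only matching characteristics, the recruitment section describes no pair formation, and Section III.D lists an unpaired test.

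A second defence is that the damage is small on average and that a data set at exactly p = 0.05 is the most sensitive case. That is also true. The range from 0.015 to 0.10 describes a borderline result, not a typical one.

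On order, counterbalancing is itself a way of handling order, and a covariate can be left to an analysis plan. With near-equal orders this largely holds, so the order term is only a secondary point.

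A reader might go further in three ways that the documents do not support.

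- H1.1 might seem affected. It is a baseline comparison, and the quoted sentences cover changes only.
- Equal orders might seem impossible with 25 per group. The counterbalancing is stated across subjects, and 25/25 among 50 is attainable; equality within each group is not promised.
- Alternation might seem to bias the target comparison. It is predictable and is not randomization, but every subject is to receive both targets, and no specific bias follows from the text.

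**Conclusion.** The point holds for the group comparison. The protocol fixes, for connectivity and again for rCMRglu, a test that cannot be run on MDD against controls without an undocumented pairing. The consequence is a result that depends on that pairing (roughly p = 0.015 to 0.10 around an unpaired p of 0.05, at 25 per group with equal variances) and the loss of controls along with lost patients.

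It would be wrong to infer an inflated false-positive rate. With a pairing fixed blind to the outcome, type I error stays near 5% and power falls by 79.2 − 77.6 = 1.6 percentage points. The error would be inflated only if the pairing were chosen after seeing the results, which nothing in the protocol suggests.

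The missing order term is a lesser point. With near-balanced orders it costs precision, by an amount that depends on an assumed period effect. Bias becomes material only if dropout unbalances the orders.

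**What to change.** In Section VI, leave the paired t-tests for within-individual change as they are (pre/post rTMS for connectivity, baseline/post rTMS for rCMRglu). Replace the two sentences on the other comparisons, for both outcomes, as follows.

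1. Changes are compared between the two targets by a within-subject (paired) analysis.
2. Changes for each target, and the target difference in changes, are compared between MDD patients and controls by an independent-samples (Welch) t-test. Alternatively, define one-to-one matched pairs before analysis, state what happens when one member is lost, and use a paired test. Choose one of the two, so that the group effect has a single test.

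Secondary: add session order to the target comparison, for example by regressing each subject's target difference on order coded ±½ and testing the intercept. This costs about one degree of freedom and makes good the statement in Section IV.A.

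Optional: replace alternation with a random list in permuted blocks within each diagnostic group, so that the order is randomized as the protocol says.

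The cost is a few sentences and, if wanted, a short list. The planned 25 per group stays; with the independent-samples test it gives 90% power for a difference of 0.94 SD.

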This study will take advantage of a novel combined MRI-PET scanner^{19,20} (the MRI-BrainPET camera) to *simultaneously* record BOLD fMRI and ¹⁸Fluorodeoxyglucose (FDG)-PET data following rTMS to DLPFC, in both depressed patients and in healthy controls. We will specifically target regions of the DLPFC which share functional associations with the sgACC. The sgACC was chosen as the main limbic region of interest because of mounting evidence for the pivotal and integrative role it plays in MDD. For instance, sgACC activity is enhanced during acute sadness⁵⁷ and reduced after anti-depressant regimens.^{58,59} Also, the sgACC is the target of deep brain stimulation (DBS) in treatment refractory MDD.^{33,60} Network dynamics in MDD will be assessed by comparing identical stimulation regimens delivered to regions correlated, and anticorrelated, with sgACC, (analogous to how we previously used two different rTMS regimens to lPpL¹⁴). Motivation for inclusion of the correlated region is self-evident based on our prior study.¹⁴ Motivation for stimulating the anticorrelated region is twofold. First, sgACC anticorrelations are rather prominent in DLPFC.^{21,22} Second, these tend to be more lateral, and thus anatomically more closely approximate the clinical stimulation target.^{17,61,62} Primary outcomes of interest will be rTMS induced changes in regional cerebral metabolic rate of glucose uptake (rCMRglu) at the DLPFC stimulation sites and in sgACC; as well as rTMS induced changes in functional connectivity between sgACC-DLPFC. Secondary outcomes will involve rTMS induced connectivity changes between sgACC and three additional cortico-limbic nodes: dmPFC⁹, NA¹⁻⁵ and amygdala.³⁰ Network dynamics will be assessed through observation of the interplay between local metabolic and network changes. While extant data⁶³ might be predictive of these dynamics (**Fig 3**), we expect that these will be revealed empirically.

[figure not shown]

Fig 3. Schematic representation of how local and distributed changes induced by rTMS to DLPFC **might** interact. (A) No rTMS, (B) 20Hz rTMS to DLPFC positively correlated to sgACC and (C) 20Hz rTMS to DLPFC anticorrelated to sgACC. In this model, 20Hz rTMS increases rCMRglu at both DLPFC sites (up arrows)⁵³⁻⁵⁵. In B, this might decrease connectivity between DLPFC and sgACC (thinned red line) and increase rCMRglu in sgACC. In C, rTMS decreases rCMRglu in sgACC and increases anticorrelation between these regions (thickened blue line).

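### The primary PET test is fixed at the voxel, within an individual, and does not match the regional primary outcome or the single average-change test used for sizing

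*Protocol*

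**What the plan says.** - **Primary outcome (Protocol, Section I, last paragraph).** The PET part of the primary outcome is the rTMS-induced change in "regional cerebral metabolic rate of glucose uptake (rCMRglu) at the DLPFC stimulation sites and in sgACC". This is a regional quantity at three places.
- **Sizing (Section III.D).** The PET calculation rests on a cited FDG-PET study that "found an average change in rCMRglu of 5.3% (SD=2.77%) following high frequency rTMS". From this, "sample sizes of 5 and 7 would be required (power, 90%; α , 0.05; unpaired and paired t-tests, respectively"). The protocol then says "we will conservatively recruit 25 subjects for each subject group".
- **Scans (Section V.C).** Each subject has one baseline PET scan without rTMS and one PET scan after rTMS in each stimulation session.
- **ROI placement (Section VI, fcMRI data).** The sgACC seed comes from published coordinates. The other seeds, including both DLPFC sites, are located individually from each subject's own correlation with sgACC.
- **PET analysis (Section VI, FDG-PET data).** Images are normalised to MNI space and smoothed. Then "Weighted linear contrasts will then be used to identify changes in rCMRglu in the cortico-limbic regions of interest described above". The next sentence reads "Relative differences in normalized rCMRglu in these ROIs between the baseline PET scan and the post-rTMS PET scan" and continues "within a given individual will be calculated on a voxel-by-voxel basis using a paired t-test". Two-sample tests then compare conditions and groups, with no statement of whether the input is a voxel or a region.

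**The concern.** The sentence fixes a unit of analysis for a primary outcome, and neither way of reading it gives the test that the rest of the protocol needs.

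Within one person there is nothing to test. Across subjects at each voxel there are many tests per region and no stated route from them to one regional answer. At the DLPFC stimulation sites the individually placed ROIs need not cover the same MNI voxels, so a voxel-level test across subjects may have few or no voxels shared by all subjects.

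Two other parts of the plan depend on a regional number. Hypothesis 2.3 uses the direction and size of FDG change at sgACC to predict connectivity change, which needs one defined value per subject. The Experimental Controls paragraph treats the absence of rCMRglu change in M1, A1 and V1 as evidence of specificity, and that check is only as good as the rule for calling a region unchanged. With the rule open, the same scans could support different statements about whether a region changed.

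**Working it through.** **1. The sizing is a single-test calculation.** Inputs from Section III.D: mean change 5.3%, SD 2.77%, alpha 0.05 (two-sided assumed), power 90%. Standardised effect d = 5.3/2.77 = 1.913. Exact noncentral-t power with one test:

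| n | paired, noncentrality d√n, df n−1 | unpaired per group, noncentrality d√(n/2), df 2n−2 |
|---|---|---|
| 5 | 88.5% | 75.5% |
| 6 | 95.8% | 84.7% |
| 7 | 98.6% | 90.7% |

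The smallest n for 90% is 6 paired and 7 per group unpaired. The stated 5 and 7 are therefore of the right order for one test of one average change. They fit better with the paired and unpaired labels exchanged, which is a separate matter. Nothing in the calculation refers to voxels.

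**2. The literal reading.** At one voxel in one person, for one condition, there is one difference (post-rTMS minus baseline). Degrees of freedom = 1 − 1 = 0. No standard deviation can be estimated, so there is no t statistic.

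**3. The per-voxel reading across subjects.** The protocol gives neither voxel size nor smoothing width, and it states the seed size in inconsistent units (a diameter in mm³). Assumptions: a sphere 8 mm in diameter and 2 mm voxels. Volume = (4/3)π·4³ = 268 mm³, and 268/8 ≈ 33 voxels. If the voxels were independent, the chance of at least one p<0.05 under the null would be 1 − 0.95³³ = 81.6%. This is an upper bound, because smoothing correlates neighbours. Simulated null trials with Gaussian-smoothed noise, n = 25 and 33 voxels (4,000 per setting) gave:

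| Smoothing (FWHM) | any voxel p<0.05, uncorrected | ROI mean, one value per subject |
|---|---|---|
| 4 mm | 59% | 5% |
| 6 mm | 40% | 5% |
| 8 mm | 30% | 5% |
| 10 mm | 24% | about 5% |
| 12 mm | 20% | about 5% |

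**4. Power at the planned sample.** Using d = 1.913, n = 25 per group and Bonferroni over m tests: with m = 33, power is above 99.9% both paired and unpaired; with m = 10,000, it is 99.8% paired and 92.8% unpaired. It drops below 90% at m = 33 only if the voxel-level SD exceeds the regional SD. At 1.5 times (an assumption) power is 99% paired and 86% unpaired. At twice it is 87% and 51%.

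**The case against.** The strongest defence has four parts.

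- **The phrase may describe only the pairing.** The fcMRI paragraph uses similar wording where the measure is one z value per ROI pair before and after rTMS, so the test there must run across subjects. This is a fair reading and probably the intended one. It answers the zero-degrees-of-freedom problem but not the mismatch of unit.
- **A regional analysis is partly described.** The voxel tests are confined to the ROIs, and ROI contrasts are named just before them. This stands, and it limits the point: the protocol does not replace a regional analysis with a whole-brain search. It leaves open which of the two analyses decides.
- **The correction threshold may sit in the statistical analysis plan.** This also stands. A missing voxelwise correction is not a fault of the protocol, and the 20-60% range applies only under a rule that the protocol does not state. The choice of unit, however, is fixed in the protocol, and a threshold would not supply a common voxel set at the DLPFC sites.
- **Power is ample.** A reader might infer that the 90% power is lost. The documents do not support that: the 90% belongs to n = 5 and 7, while 25 per group are planned, and at the protocol's own effect power stays above 90% even after Bonferroni over 10,000 voxels.

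A reader might also infer that voxels within one person are to serve as replicates, which would inflate error badly. The text does not say this. Voxel by voxel ordinarily means a separate test at each voxel, and pooling voxels is a different analysis.

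**Conclusion.** The point holds as a mismatch in the unit of analysis for a primary outcome. The PET comparison cannot be run as literally written. As a test per voxel across subjects, it fits neither the regional outcome in Section I nor the single average-change test in Section III.D, and it has no assured common voxels at two of the three primary locations. Which analysis decides the primary outcome is not stated.

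The size depends on a decision rule that the protocol leaves open. If any uncorrected voxel at p<0.05 sufficed, the null error rate per ROI would be roughly 20-60%, against 5% for an ROI mean. This rests on assumed 2 mm voxels, an 8 mm sphere, 4-12 mm Gaussian smoothing and n = 25. With a suitable correction the inflation goes away, but the mismatch of unit remains. No loss of power at 25 per group is claimed. The change is worth making before analysis, and it needs no new data.

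**What to change.** In Section VI, FDG-PET data:

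1. Define the primary PET measure as the mean normalised rCMRglu per subject, session and ROI, using each subject's own two DLPFC sites and sgACC.
2. Test its change from baseline across subjects, with the subject as the unit. This is the type of test that Section III.D sizes.
3. Use the same measure for the comparisons between conditions and between groups, and for Hypothesis 2.3.
4. Reword the phrase about a given individual so that it describes only the pairing of scans.
5. Make the voxelwise maps secondary, with multiplicity correction. The details can be left to the statistical analysis plan.

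The cost is a few lines of wording and a simpler analysis. The downside is less spatial detail in the primary result, though the secondary maps still provide it.
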